8.2.5 Data management

The investigators are required to prepare and maintain adequate and accurate case histories designed to record all observations and other data pertinent to the investigation on each individual treated in the investigation. Data that are derived from source documents and reported on the CRF must be consistent with the source documents or the discrepancies must be explained. OnCore will be the designated electronic data capture tool. All data should be entered onto OnCore within 2 weeks of each study visit. AEs need to be entered within 72 hours and SAEs need to be entered within 24 hours of the site becoming aware of the event.

8.3 RECORDS**8.3.1 Source documents**

Source documents provide evidence for the existence of the patient and substantiate the integrity of the data collected. Source documents are filed at the investigator's site.

Data entered in the (e)CRFs that are transcribed from source documents must be consistent with the source documents or the discrepancies must be explained. The investigator may need to request previous medical records or transfer records, depending on the study; also current medical records must be available.

For (e)CRFs all data must be derived from source documents.

8.3.2 Direct access to source data and documents

The sponsor will allow access to all source data and documents for the purposes of monitoring, audits, IRB review, and regulatory inspections. Source documents provided to the coordinating

center for the purpose of auditing or monitoring will be de-identified and labeled with the study number, patient ID number, and patient initials. Upon inquiry, NCCN and Boehringer Ingelheim will be provided access to de-identified source data and documents pertaining to data resulting from patients on this study.

The study monitor or other authorized representatives of the sponsor may inspect all documents and records maintained by the participating investigators, including but not limited to medical records and pharmacy records for the patients in this study. The clinical study site will permit access to such records.

8.3.3 Storage of records

U.S. FDA regulations (21 CFR §312.62[c]) require that records and documents pertaining to the conduct of this study and the distribution of investigational drug, including CRFs, consent forms, laboratory test results, and medication inventory records, must be retained by the Principal Investigator for 2 years after marketing application approval. If no application is filed, these records must be kept 2 years after the study is discontinued and the U.S. FDA and the applicable national and local health authorities are notified.

8.4 LISTEDNESS AND EXPEDITED REPORTING OF ADVERSE EVENTS

8.4.1 Listedness

To fulfil the regulatory requirements for expedited safety reporting, the sponsor evaluates whether a particular adverse event is "listed", i.e. is a known side effect of the drug or not. Therefore, a unique reference document for the evaluation of listedness needs to be provided. For afatinib this is the current version of the Investigator's Brochure. No AEs are classified as listed for matching placebo, study design, or invasive procedures.

8.4.2 Expedited reporting to health authorities and IECs/IRBs

Expedited reporting of serious adverse events, e.g. suspected unexpected serious adverse reactions (SUSARs), to health authorities and IRB or Ethics Committees will be done according to local regulatory requirements. Further details regarding this reporting procedure are provided in the Investigator Site File.

8.5 STATEMENT OF CONFIDENTIALITY

Individual patient medical information obtained as a result of this study is considered confidential and disclosure to third parties is prohibited with the exceptions noted below. Patient confidentiality will be ensured by using patient identification code numbers.

Treatment data may be given to the patient's personal physician or to other appropriate medical personnel responsible for the patient's welfare. Data generated as a result of the study need to be available for inspection on request by the participating physicians, the sponsor's representatives, by the IRB or Ethics Committees and the regulatory authorities.

8.6 END OF TRIAL

The trial will end when the last patient has completed the last EOR visit or follow-up for progression visit, depending on whether that last patient progressed on treatment.

8.7 PROTOCOL VIOLATIONS

YCCI will conduct ongoing monitoring of the study records of each participant accrued at each site throughout the course of the study in order to ensure proper conduct of this study and identify in a timely manner any protocol violations, as described in Section 8.2.1. Protocol violations will be reported to site's IRBs in accordance with institutional policy.

8.8 COMPENSATION AVAILABLE TO THE PATIENT IN THE EVENT OF TRIAL RELATED INJURY

No monetary or financial compensation will be made available to study patients in the event of study related injury. However, reasonable medical care will be provided for treatment related injury. Subjects or their insurance providers will be responsible for costs related to treatment of study related injury.

10. APPENDICES

10.1 APPENDIX 1

List of potent inhibitors and inducers of P-glycoprotein (MDR1)

Inhibitors	Inducers
Amiodarone	Carbamazepine
Azithromycin	Phenytoin
Captopril	Rifampicin
Carvedilol	St John's Wort
Clarithromycin	Phenobarbital Salt
Conivaptan	Tipranavir
Cyclosporine	Ritonavir
Diltiazem	
Dronedarone	
Erythromycin	
Felodipine	
Itraconazole	
Ketoconazole	
Lopinavir	
Nelfinavir	
Ritonavir	
Quinidine	
Ranolazine	
Saquinavir	
Tacrolimus	
Ticagrelor	
Verapamil	

As the information on potent inhibitors and inducers of P-glycoprotein may evolve, it is important for the investigator to assess such status on concomitant therapies and in case of questions contact the sponsor.

10.2 APPENDIX 2 COCKCROFT-GAULT FORMULA

The following formula may be used for estimated creatinine clearance rate (eC_{CR}) using Cockcroft-Gault formula. The use of on-line calculators or formulas which are institution standards for eC_{CR} and differ slightly may also be used. The calculations and results must be filed in the patient's chart.

When serum creatinine is measured in mg/dL;

$$eC_{CR} = \frac{(140 - \text{Age}) \cdot \text{Mass (in kilograms)} \cdot [0.85 \text{ if Female}]}{72 \cdot \text{Serum Creatinine (in mg/dL)}}$$

When serum creatinine is measured in $\mu\text{mol/L}$;

$$eC_{CR} = \frac{(140 - \text{Age}) \cdot \text{Mass (in kilograms)} \cdot \text{Constant}}{\text{Serum Creatinine (in } \mu\text{mol/L)}}$$

Where *Constant* is 1.23 for men and 1.04 for women.

10.3 APPENDIX 3

ECOG PERFORMANCE STATUS

ECOG PERFORMANCE STATUS*	
Grade	ECOG
0	Fully active, able to carry on all pre-disease performance without restriction
1	Restricted in physically strenuous activity but ambulatory and able to carry out work of a light or sedentary nature, e.g., light house work, office work
2	Ambulatory and capable of all self-care but unable to carry out any work activities. Up and about more than 50% of waking hours
3	Capable of only limited self-care, confined to bed or chair more than 50% of waking hours
4	Completely disabled. Cannot carry on any self-care. Totally confined to bed or chair
5	Dead

10.4 APPENDIX 4 RECIST 1.1 CRITERIA

The criteria below are based on RECIST 1.1 (9).

The preferred method of assessment is a spiral CT scan with IV and oral contrast, unless IV and/or oral contrast are medically contraindicated. CT scans of the chest, abdomen and other areas of known or newly suspected disease must be performed. Scans of the abdomen, pelvis and other areas of the body, but not chest, may be done with MRI instead of CT.

Skin lesions followed as target lesions must be documented by color digital photography and must include in the image a ruler with millimeter subdivisions and a label that includes the patients ID and date.

Bone scans (using ^{99}m -technetium polyphosphonate scintigraphy) are recommended at baseline if the patient has any signs and symptoms consistent with bone metastasis or a history of bone metastasis. Bone metastasis identified at baseline must be documented and assessed according to RECIST 1.1 at the times of the other tumor measurements indicated in the flow chart. During the study bone scans should be repeated as clinically indicated in patients without bone metastasis at Baseline.

For the purposes of this study, patients should be re-evaluated for response at weeks 8, 16 and every 8 weeks thereafter. In the event of a treatment delay, interruption or discontinuation of treatment, tumor assessment should continue to follow the original schedule.

Follow-up tumor assessments must utilize the same CT/MRI/photographic method and acquisition technique (including use or non-use of IV contrast) as were used for screening assessments to ensure comparability. A chest x-ray or skeletal x-ray which clearly demonstrates a new metastatic lesion may be used to document progression in lieu of CT/MRI/bone scan.

Only those patients who have measurable disease present at baseline, have received at least 3 weeks of therapy, and have had their disease re-evaluated will be considered evaluable for response. These patients will have their response classified according to the definitions stated below.

Measurability of tumour at baseline**Measurable lesions**

Lesions that can be accurately measured in at least one dimension with longest diameter ≥ 10 mm (by CT scan, MRI, caliper measurement) or ≥ 20 mm (by chest X-ray). Pathological lymph nodes, defined as lymph nodes with a short axis >15 mm are also measurable.

Measurable disease

Measurable disease requires the presence of at least one measurable lesion. Measurable lesion if limited to either small (<2cm) solitary visceral lesion or scant (<5cm) lymph nodes only metastasis should be evaluated for additional evidence of malignant nature and discussed with the sponsor before enrolling.

Non-measurable disease

Non-measurable lesions are all other lesions, including small lesions (longest diameter <10 mm with CT scan, MRI or caliper measurement or <20 mm with chest X-ray or pathological lymph nodes with shortest axis \geq 10 and <15 mm) as well as truly non-measurable lesions. Lesions considered truly unmeasurable include leptomeningeal disease, ascites, pleural or pericardial effusion, inflammatory breast disease, lymphangitic involvement of skin or lung, abdominal masses/ abdominal organomegaly identified by physical exam that is not measurable by reproducible imaging techniques.

New lesions in irradiated fields

Previously irradiated lesions should not be used as indicator lesions. However, new lesions occurring in previously irradiated fields can be used to assess the antitumor response.

Methods of measurement

All measurements must be recorded in metric notation, using a ruler or callipers. All baseline evaluations must be performed as close as possible to the treatment start and never more than 4 weeks before the beginning of the treatment. If a lesion is considered too small to measure, a default measurement of 5mm should be applied. If the lesion is not visible, a default measurement of 0mm should be applied.

The same method of assessment and the same technique must be used to characterise each identified and reported lesion at baseline and during follow-up.

Clinical lesions will only be considered measurable when they are superficial (e.g., skin nodules, palpable lymph nodes). In the case of skin lesions, documentation by colour photography including a ruler to estimate the size of the lesion is obligatory.

CT and MRI are the best currently available and reproducible methods to measure target lesions selected for response assessment. Conventional CT and MRI should be performed with cuts of 5 mm or less in slice thickness contiguously. Spiral CT should be performed using a 5 mm contiguous reconstruction algorithm. This applies to the chest, abdomen and pelvis.

Ultrasound, endoscopy and laparoscopy should not be used to measure tumour lesions or evaluate tumour response. However, these techniques can be useful to supplement information from other techniques.

Cytology and histology can be used to differentiate between PR and CR in rare cases (for example, residual lesions in tumour types such as germ cell tumours where known residual benign tumours can remain).

Baseline Documentation of Target and Non-target Lesions

All measurable lesions up to a maximum of two lesions per organ and five lesions in total, representative of all involved organs should be identified as target lesions and will be recorded, measured (longest diameter = LD) and numbered at baseline. Target lesions should be selected on the basis of their size (lesions with the longest diameter) and their suitability for accurate repetitive measurements (either by imaging techniques or clinically). Lymph nodes must be $\geq 15\text{mm}$ in order to be considered as target lesions.

A sum of the longest diameter (LD) for all target lesions will be calculated and reported as the baseline sum LD. The baseline sum LD will be used as reference to further characterise the objective tumour response of the measurable dimension of the disease (see Table 10.4:1).

Table 10.4: 1 Evaluation of target lesions

Complete Response (CR)	Disappearance of all target lesions.
Partial Response (PR)	At least a 30% decrease in the sum of LD of target lesions taking as reference the baseline sum LD.
Progression (PD)	At least a 20% increase in the sum of LD of target lesions taking as reference the smallest sum LD recorded since the treatment started, together with an absolute increase in the sum of LD of at least 5mm. OR The appearance of one or more new lesions.
Stable Disease (SD)	Neither sufficient shrinkage to qualify for PR, taking as reference the baseline SoD, nor sufficient increase to qualify for PD taking as reference the smallest SoD since the treatment started.

All other lesions (or sites of disease) should be identified as non-target lesions and should also be recorded at baseline. Measurements are not required and these lesions should be followed as "present" or "absent" (see Table 10.4:2).

Table 10.4: 2

Evaluation of non-target lesions and new lesions

Complete Response (CR)	Disappearance of all non-target lesions and normalisation of tumour marker level. All lymph nodes must be non-pathological in size (<10 mm short axis)
Non-CR/Non-PD	Persistence of one or more non-target lesions or/and maintenance of tumour marker level above normal limits.
Progression (PD)	Appearance of one or more new lesions and/or unequivocal progression of existing non-target lesions. Although a clear progression of non-target lesions only is exceptional, in such circumstances, the opinion of the treating physician should prevail and the progression status should be confirmed later by the review panel (or study chair).

In some circumstances it may be difficult to distinguish residual disease from normal tissue. When the evaluation of complete response depends upon this determination, it is recommended that the residual lesion be investigated (fine needle aspirate/biopsy) before confirming the complete response status.

Confirmation

In case of tumour response (CR or PR), confirmation will be performed with a repeat assessment no less than 4 weeks after the RECIST criteria for response have been met. In the case of SD, measurement must have met the SD criteria at least once after study entry at an interval of not less than 6 weeks.

Evaluation of best response to study treatment

The best response to study treatment (Table 10.4: 3) is the best response recorded from the start of treatment until disease progression or start of further anti-cancer treatment (taking as reference for progressive disease the smallest measurements recorded since the treatment started). In general, the patient's best response assignment will depend on the achievement of both measurements and confirmation criteria (Table 10.4: 3).

Patients with a global deterioration of health status requiring discontinuation of treatment without objective evidence of disease progression at that time should be reported as "symptomatic deterioration". Every effort should be made to document the objective progression even after discontinuation of treatment.

Table 10.4: 3 Algorithm for evaluation of overall response

Target lesions	Non-target lesions	New lesions	Overall response
CR	CR	No	CR
CR	Non-CR/ Non-PD	No	PR
CR	Not evaluated	No	PR
PR	Non-PD or not evaluated	No	PR
SD	Non-PD or not evaluated	No	SD
Not evaluated	Non-PD	No	NE
PD	Any	Yes or No	PD
Any	PD	Yes or No	PD
Any	Any	Yes	PD

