a: Screening history, concomitant medications, physical exam, height, weight, vitals, performance status and laboratory evaluations (including pregnancy test) should be obtained within 2 weeks prior to treatment initiation. Screening EKG and CT scans or MRI should be obtained within 28 days prior to treatment initiation.

b: Tumor sample for correlative analyses can be archival or fresh, should be since the last systemic treatment administered and should be obtained where feasible.

Repeat tumor biopsy to be obtained at end of cycle 1 (4 weeks after treatment initiation, with a window of +1 week), where medically feasible

c: Coagulation studies recommended every 4 weeks (+/- 3 days) only for patients on anticoagulation therapy (excluding a daily baby aspirin).

d: Restaging scans for tumor assessment as appropriate for site of disease to be obtained at end of cycle 2 (8 weeks +/- 3 days), and then every 8 weeks thereafter (+/- 3 days) through the EOR visit, or EoFU visit for patients who discontinued treatment for reasons other than disease progression

e: Repeat tumor biopsy for correlative analyses to be obtained where medically feasible at disease progression or EOT.

f: EOT visit within 7 days of discontinuation from study treatment period.

g: EOR visit at 30 days (window of + 2 weeks) after discontinuation from study treatment period.

h: Additional f/u visits for disease progression to continue every 4 weeks (with a window of +7 days) for a maximum of 24 weeks for patients who discontinued study treatment for reasons other than disease progression.

i: Last visit for disease progression assessment. Follow-up period will continue until progression, start of new anti-cancer therapy, or a max of 24 weeks, whichever comes first. The EoFU visit will be performed within 2 weeks of known progression, start of new anti-cancer therapy, or completion of predefined follow-up progression period.

j: Monthly (+/- 1 week) telephone f/u for survival (to continue until death).

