5. VARIABLES AND THEIR ASSESSMENT

5.1 TRIAL ENDPOINTS

5.1.1 Primary endpoint(s)

Objective Response Rate (Complete Response + Partial Response), defined by tumor shrinkage (mm), per Response Evaluation Criteria in Solid Tumors (RECIST) v1.1.

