7.2 DETERMINATION OF SAMPLE SIZE

The sample size calculation was based on the primary endpoint, the objective response rate. Historical data with single agent Cetuximab have yielded response rates of 10-15%, as discussed in Section 1.1. We used Software PASS 2012 (Kaysville, UT) **Inequality Tests for One Proportion** module for sample size calculation. The results were shown in the tables and figures below for different historical control rate. A sample size of 33 will allow us to detect an absolute difference of 20% (alternative hypothesis 30% - null hypothesis 10%) in ORR using a two-sided binomial test with 80% power and significance level of 0.05. Should the historical ORR be 15% (null hypothesis), a sample size of 34 will achieve 80% power to detect an absolute difference of 20% in ORR too.

Null hypothesis: ORR=10%

Null hypothesis: ORR=15%

Based on the calculation as above, we plan to enroll 50 patients which provide us 80% power to detect an alternative hypothetical ORR of 24% by rejecting a null hypothesis of 10%. This

sample size will achieve 80% power to detect an absolute difference of 18% if the historical control of ORR is 15% (i.e. 33% vs. 15%).

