7.3 PLANNED ANALYSES

All statistical analyses will be performed using the SAS statistical software, version 9.4 (SAS Institute Inc., Cary, NC). Significance level will be set as $p < 0.05$, two-sided. Yale Center for Analytical Sciences will provide statistical support.

Patient demographics and clinical characteristics will be summarized. The primary analysis will use a 2-sided binomial test to compare the ORR with historical control of 10%. 95% confidence interval of ORR will be reported as well. As an exploratory analysis, Logistic regression will be used to identify potential risk factors that are associated with ORR.

The secondary endpoint is progression-free survival and overall survival with 1 year follow-up. We will use Kaplan-Meier survival analysis to estimate the median PFS and OS in the cohort. Additional Cox regression analyses will be carried out to examine the association between demographical or clinical variables and survival outcome.

We expect 10 – 15 HPV + patients will be enrolled. We will compare the demographics and clinical characteristics between HPV + and HPV - subgroup, and then calculate the ORR by HPV status. An exploratory analysis will be conducted to compare the ORR using multivariate logistic regression, and a survival analysis for the secondary endpoint as well.

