7.4 HANDLING OF MISSING DATA

We will perform complete case analyses in which those with missing data will be excluded from the relevant analyses. We will not impute missing data. Missing data on one item will not preclude a patient's observed data from being used in other analyses. For example, a patient might have missing response data but observed toxicity data. The toxicity data can be used in appropriate analyses.

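### The primary ORR has no stated denominator, and the only rules in the plan lead to an evaluable-only one that drops early non-responders and shifts the ORR upward

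*Combined protocol and SAP*

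**What the plan says.** - **Endpoint, section 5.1.1.** "Objective Response Rate (Complete Response + Partial Response), defined by tumor shrinkage (mm), per Response Evaluation Criteria in Solid Tumors (RECIST) v1.1". No denominator is given.
- **Primary test, section 7.3.** "The primary analysis will use a 2-sided binomial test to compare the ORR with historical control of 10" per cent. No analysis set is named there or in the synopsis, and no all-enrolled or all-treated set is defined for this trial. Section 1.1 uses the term intent-to-treat only for the group's earlier study.
- **Evaluability, Appendix 10.4.** Only patients with measurable disease at baseline who "have received at least 3 weeks of therapy, and have had their disease re-evaluated will be considered evaluable for response". Response is classified in these patients. The overall-response table includes an NE category, and nothing says how NE enters the ORR.
- **Missing data, section 7.4.** "We will perform complete case analyses in which those with missing data will be excluded from the relevant analyses". There is no imputation, and the illustration is a missing response: "For example, a patient might have missing response data but observed toxicity data".
- **Scans after stopping.** Appendix 10.4: "In the event of a treatment delay, interruption or discontinuation of treatment, tumor assessment should continue to follow the original schedule". Flow Chart note d continues restaging "through the EOR visit, or EoFU visit for patients who discontinued treatment for reasons other than disease progression".
- **Sample size, section 7.2.** "we plan to enroll 50 patients which provide us 80% power to detect an alternative hypothetical ORR of 24" per cent against 10%. No allowance for unevaluable patients is mentioned.

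**The concern.** Whether a patient is evaluable is settled after baseline, partly by how the disease behaves. Followed as written, the rules remove two groups:

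- patients with less than 3 weeks of therapy, even if progression is documented;
- patients who die, deteriorate or are lost before any re-evaluation.

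Someone never re-evaluated cannot be a responder. Someone with under 3 weeks of therapy is very unlikely to be one, since Appendix 10.4 also requires confirmation at least 4 weeks after the criteria are first met. The numerator therefore hardly changes while the denominator shrinks, and the ORR and its confidence interval move up.

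The documents make early loss plausible. The first scheduled response scan is at week 8. The phase III trial cited in section 1.1 had median PFS of 2.6 months (afatinib) and 1.7 months (methotrexate). ECOG 2 is allowed, and section 3.1 lets treatment stop on clinical examination alone. Because response is assessed by the investigator in an open-label single-arm trial, an unnamed denominator also leaves the pass/fail result open to choice after the responses are known.

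**Working it through.** **Inputs.** Null 10%, alternative 24%, n=50, two-sided 5% (sections 7.2 and 7.3). The unevaluable share is not in the documents, so it is varied. Assumptions: every excluded patient is a non-responder, and the test is exact with 2.5% in the upper tail.

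**1. The plan's own figure.** The cutoff c(n) is the smallest c with P(X ≥ c | n, 0.10) ≤ 0.025. For n=50, c=10: the upper tail is 0.0245 and power is P(X ≥ 10 | 50, 0.24) = 0.793. The stated 80% reproduces when all 50 patients are analysed.

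**2. Cutoffs with fewer patients.** c=10 for n=44-50, c=9 for n=37-43, c=8 for n=35-36.

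**3. False-positive rate.** If the all-treated ORR is 10%, the rate among n evaluable patients is 0.10 × 50/n = 5/n. The error is P(X ≥ c(n) | n, 5/n):

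| Excluded of 50 | n | c | Evaluable ORR | Error |
|---|---|---|---|---|
| 0 | 50 | 10 | 10.0% | 2.45% |
| 1 | 49 | 10 | 10.2% | 2.44% |
| 6 | 44 | 10 | 11.4% | 2.35% |
| 7 | 43 | 9 | 11.6% | 5.61% |
| 13 | 37 | 9 | 13.5% | 5.41% |
| 14 | 36 | 8 | 13.9% | 11.73% |
| 15 | 35 | 8 | 14.3% | 11.68% |

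The steps come from discreteness: the error moves only when the cutoff does. Averaging over a Binomial(50, s) number of unevaluable patients smooths this: 2.5%, 3.0%, 5.7% and 9.6% at s = 5%, 10%, 20% and 30%.

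**4. A result that flips.** Two-sided p as twice the upper tail, Clopper-Pearson intervals:

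- 9/50 = 18.0%: p = 2 × 0.0579 = 0.116, 95% CI 8.6-31.4%. Fails.
- 9/43 = 20.9%: p = 2 × 0.0244 = 0.049, 95% CI 10.04-36.0%. Passes.
- 9/44 = 20.5%: p = 0.056. Fails, so 7 exclusions is the flip point.
- 10/50 = 20.0%: p = 0.049. Passes.

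**5. Other two-sided convention.** The plan does not say how the two-sided exact p is formed. With the minimum-likelihood form the cutoff is 10 for n=48-50 and 9 for n=38-47, so 9/47 already passes (p=0.048). The upper-tail error at n=47 is P(X ≥ 9 | 47, 5/47) = 5.7%. Of that, P(X ≥ 9 | 47, 0.10) = 4.1% would arise with no exclusion bias, so exclusion itself adds about 1.6 points.

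**6. Power.** If 24% is the all-treated rate, 10 exclusions give an evaluable rate of 12/40 = 30%, and apparent power rises to 0.889. If 24% is meant for evaluable patients, power falls to 0.666, 0.648 and 0.627 at n=45, 40 and 35.

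**7. If the historical 10% is itself evaluable-only**, with the same unevaluable share of 10%, 20% or 30%:

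- the evaluable-only test has error 1.57%, 1.62% and 1.52%, so no inflation;
- the all-50 test against 10% has error P(X ≥ 10 | 50, 0.10(1−s)) = 1.3%, 0.6% and 0.2%, so it is conservative. If 24% is also an evaluable rate, its power is 66%, 50% and 33%.

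**The case against.** The strongest reply is that the evaluable-only denominator is inferred. Appendix 10.4 says whose response is classified and never mentions the ORR denominator, and powering on all 50 suggests that all 50 were to be counted. That no sentence states the denominator is true, and it is part of the problem. The handling rules nevertheless point one way, and nothing in the plan counts an unassessed patient as a non-responder.

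The dropped group may also be small. Scans continue after treatment stops, imaging is possible at the EOT and EOR visits, an x-ray can document progression, and symptomatic deterioration is a recorded outcome. This stands in part. Patients with at least 3 weeks of therapy who are re-evaluated stay in, including progressors and early stoppers. But these provisions do not override the 3-week condition, and they cannot help patients who die first.

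Next, the harm depends on an unknown share. With equal tails, 1 to 6 exclusions (up to 12%) do not inflate the error, although the point estimate still rises. The 5.7% under the minimum-likelihood form at n=47 is mostly due to that convention. Both points stand and limit the size of the concern.

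Last, if the historical 10% was evaluable-only, testing all treated patients against it is conservative and costs power (step 7). This stands as a reason to state the source of the 10%. It does not justify leaving the trial's own denominator open. Nor does the trial's exploratory label in section 2.1, since section 7.3 sets a formal pass/fail test.

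**Conclusion.** The concern holds. The primary ORR has no stated denominator, and Appendix 10.4 with section 7.4 leads to an evaluable-only one that removes almost only failures, while the stated power corresponds to analysing all 50. The upward direction is close to certain; the size cannot be computed from the documents. With a true all-treated ORR of 10% and excluded patients all non-responders, the equal-tail false-positive rate stays at about 2.4% for up to 6 exclusions, more than doubles from 7, and reaches about 11.7% at 14 or 15. Part or all of this cancels if the historical 10% was calculated in the same way, which the documents do not say. Because the choice can turn a failed primary test into a pass, it must be fixed before the responses are analysed.

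**What to change.** Amend sections 7.3 and 7.4 and Appendix 10.4 as follows:

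1. Define the primary ORR denominator as all patients who received at least one dose of study treatment.
2. Count any patient without a documented response per Appendix 10.4, including those never re-evaluated, as a non-responder.
3. Exempt the primary ORR from the complete-case rule in section 7.4.
4. Report the ORR among patients with at least 3 weeks of therapy and a re-evaluation as a sensitivity analysis.
5. State the denominator behind the historical 10%, or say that it is unknown, so that the comparison can be judged.

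With 50 treated, success is 10 or more responders under either two-sided convention, and power at an all-treated ORR of 24% stays at 79.3%. The cost is wording only, with no new data. The reported ORR will be equal or lower, and the test will be conservative if the historical 10% proves to be evaluable-only.

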5.2 ASSESSMENT OF EFFICACY

Response and progression will be evaluated in this study using Response Evaluation Criteria in Solid Tumors (RECIST) guideline (version 1.1) (9). Tumor response will be assessed by investigator.

See APPENDIX 10.4, RECIST 1.1 Criteria for details on lesion measurements and response assessment.

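### Appendix 10.4 sizes lymph nodes by short axis but scores target nodes by longest diameter, so the response rule behind the primary endpoint does not fit its own nodal definitions

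*Combined protocol and SAP*

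**What the plan says.** Section 5.1.1 makes objective response rate (CR + PR) the primary endpoint, and Section 7.3 tests it against 10%. Section 5.2 sends the assessor to the appendix: "See APPENDIX 10.4, RECIST 1.1 Criteria for details on lesion measurements and response assessment". After setting out who is evaluable, Appendix 10.4 adds: "These patients will have their response classified according to the definitions stated below". The appendix is therefore the working rule.

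On nodes, the appendix uses short axis three times:

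- Measurable lesions: "Pathological lymph nodes, defined as lymph nodes with a short axis >15 mm are also measurable".
- Non-measurable disease: this includes "pathological lymph nodes with shortest axis" of at least 10 and under 15 mm.
- Table 10.4:2, CR row for non-target lesions: nodes must be under 10 mm in short axis to count as non-pathological.

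On scoring, it uses the other axis. Target lesions "will be recorded, measured (longest diameter = LD) and numbered at baseline", and the baseline reference is their sum: "A sum of the longest diameter (LD) for all target lesions will be calculated and reported as the baseline sum LD". In Table 10.4:1, CR is "Disappearance of all target lesions" and PR is "At least a 30% decrease in the sum of LD of target lesions taking as reference the baseline sum LD". Neither row treats nodes separately. Table 10.4:3 carries a target SD through to an overall SD.

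**The concern.** A node enters the study on its short axis and is called normal on its short axis, but its change is scored on its length. The two can disagree. By the appendix's own cut-offs, a patient's target nodes may all have returned to normal size while the target response is still SD, which the primary endpoint counts as a failure. Nor can such a patient be a target CR, since a normal-sized node has not disappeared.

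The case is foreseeable: the appendix provides for patients whose metastatic disease is confined to lymph nodes. For them this rule alone settles the target response. Response is assessed by the investigator (Section 5.2), so an unreconciled rule may also be applied differently from patient to patient.

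**Working it through.** **The plan's own figure.** Section 7.2 states 80% power with 50 patients for 24% against 10%, two-sided 5%. The exact binomial test rejects at 10 or more responders (upper tail 0.0245) and has power 0.793 at 24%. The stated figure is reproduced, and nothing below changes it.

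**Inputs from Appendix 10.4.** Node measurable above 15 mm short axis; non-pathological below 10 mm short axis; target PR is a fall of at least 30% in summed longest diameter (LD). All node dimensions below are assumed, written short x long axis in mm; the documents give none. Non-target lesions are taken as not progressing, with no new lesions.

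1. *What the cut-offs imply.* From above 15 to below 10 mm, the short axis falls by more than 1 - 10/15 = 33.3%.
2. *One node, 16x28 to 9x20.* Short axis: (16 - 9)/16 = 43.8% fall. LD: (28 - 20)/28 = 28.6% fall. PR needs LD of at most 0.7 x 28 = 19.6 mm. Result: SD, though the node is non-pathological.
3. *Two nodes, 16x28 and 17x30 to 9x20 and 9x22.* Sum LD 58 to 42: 16/58 = 27.6% fall (PR needs at most 0.7 x 58 = 40.6). Short-axis sum 33 to 18: 45.5% fall. Result: SD.
4. *When it happens.* For a single node, SD requires final LD above 0.7 of baseline LD. Equivalently, the ratio of long to short axis must grow by a factor above 0.7 x (baseline short axis)/(final short axis): 1.07 for 15.1 to 9.9 mm, 1.24 for 16 to 9 mm, 1.56 for 20 to 9 mm. The node in step 2 goes from 28/16 = 1.75 to 20/9 = 2.22, a factor of 1.27.
5. *Proportional shrinkage.* 16x28 to 9x15.75 (28 x 9/16 = 15.75) is a 43.8% fall on both axes: PR either way.
6. *CR wording alone.* 16x28 to 9x18: LD falls (28 - 18)/28 = 35.7%, so PR is recorded where a nodal size rule would give CR. ORR counts both, so it is unchanged.
7. *The other direction.* 16x30 to 14x20: LD falls (30 - 20)/30 = 33.3% (PR); short axis falls (16 - 14)/16 = 12.5% (SD). Here LD adds a responder.
8. *Non-nodal targets present.* Node 16x24 to 9x13.5 with a stable 40 mm lesion: LD 64 to 53.5, a 16.4% fall; with short axis for the node, 56 to 49, a 12.5% fall. SD both ways, so the axis is not the cause.

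**The case against.** The best defence is that qualifying a node on one axis and tracking it on the other is unusual but can be applied consistently, and that no passage promises at least PR to a node that has become normal. That stands in part: the documents never state a short-axis sum, so outside the case of nodes that have become non-pathological, differences in PR or PD show sensitivity to the axis, not error.

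A second defence is that the line in Table 10.4:2 speaks of every lymph node, so it might cover target nodes too. But it sits in the CR row of the non-target table, and it leaves both the disappearance requirement and the LD-based PR rule in Table 10.4:1 as they are. Nor does naming RECIST 1.1 settle the matter, because Section 5.2 relies on this appendix for the measurement details.

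Third, the examples are constructed, and small node-only disease is flagged in the appendix for further evidence of malignancy and discussion with the sponsor before enrolment. That may make such patients fewer; it does not exclude them.

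A reader might infer that the rule biases ORR downward. The documents do not support this: step 7 goes the other way, and neither the share of patients with nodal targets nor the way nodes were recorded is given. A reader might also point to the test boundary: with 50 analysed, 9 responders do not reject (two-sided exact p = 0.092, or 0.116 by doubling) and 10 do (0.030, or 0.049). That is true of any single misclassification from any source and does not measure this one.

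**Conclusion.** The inconsistency is real and lies in the rule that defines the primary endpoint. As written, a patient whose only targets are nodes, all now below 10 mm in short axis, cannot be a target CR, and is a non-responder if summed LD has fallen by less than 30%. This rests on LD shrinking proportionally less than short axis. The repeat assessment required for CR or PR does not rescue the patient if the nodes stay the same size; a later scan does if summed LD then reaches a 30% fall.

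Each reclassified patient moves ORR by 1/50 = 2 percentage points if all 50 are analysed. The number of such patients, and the net direction, cannot be found from the documents and may be zero. The sample size and stated power are unaffected. The point calls for a correction before the primary analysis; it does not show that the result will be wrong.

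**What to change.** Before the primary analysis, reconcile Table 10.4:1 with the appendix's own nodal definitions:

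- Define one sum of diameters, short axis for nodal targets and longest diameter for non-nodal targets, and use it in every row. This also replaces the undefined abbreviation SoD in the SD row.
- Define target CR as disappearance of all non-nodal targets with every target node under 10 mm in short axis.
- State one nodal cut-off, with its axis, under Measurable lesions, Non-measurable disease and Baseline Documentation. At present the first says above 15 mm short axis, while the target-lesion rule says at least 15 mm and names no axis.
- Check how nodal targets were actually recorded. Where both axes are already on file, report ORR under both conventions as a sensitivity analysis.

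The cost is appendix wording, a data check and a small amount of extra analysis. No new imaging, additional reader or mandatory re-read of all scans is needed. The sponsor should accept in advance that ORR could move in either direction.
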